# 11. STUDY PROCEDURES

#### 11.1 Recruitment

Patients booked for a colonoscopy will be screened prior to their procedure to identify potentially eligible participants. Recruitment will be carried out by suitably qualified members of the research team including research nurses, research fellows and consultants.

## **11.2 Screening and Enrolment**

Patients will be approached and provided with information regarding the study to include a Patient Information Sheet (PIS). This, along with an invitation letter, will be posted to eligible participants by members of the research team with at least 1 week notice, where possible. If it is not possible to provide this notice, given the study does not alter standard treatment, patients would be approached on the day of the procedure instead. Each potential participant will be given as much time as they require to read and consider the information and ask questions to make an informed decision.

Patients who wish to participate will be able to provide informed consent to participate on the day of, and prior to, the procedure. Consent will be recorded on a paper form and obtained by a suitably qualified and delegated member of the local Research Team, in addition to the standard consent required for the procedure. There will be no financial remuneration for participating in the trial.

### 11.3 Randomisation

Participants will be randomised electronically in a 1:1 ratio into two groups. The intervention group will have their colonoscopy performed with the assistance of the WISE VISION® CAD system, the control arm will have standard colonoscopy. Randomisation will be carried out prior to the procedure being started. The randomisation will be stratified by site to ensure an equal allocation in each centre. Additionally, a blocked randomisation, with varying block sizes, will be performed to allow for a balance between groups throughout the trial.

The randomisation process will be managed using the built-in module within the project's REDCap eCRF database managed by Portsmouth Hospitals University NHS Trust. The Data Manager will generate the randomisation allocation table using statistical software, which will then be uploaded into REDCap before the first patient is consented.

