## 10. SAMPLING

- This is powered as a superiority trial.
- For computer aided detection, the ADR of competent but non-expert endoscopists is assumed to be 20% and we believe that CADe will increase it to 30% (expert level). In order to demonstrate a difference of 10% between the two groups with an 80% power and a significance level (alpha) 0.05; we will need 588 patients (294 per group). We will over recruit by 10% (max total of 654) to allow for drop outs, poor bowel prep, incomplete dataset etc. Interim analysis will be done after 50% recruitment
- For computer aided diagnosis, the NPV of endoscopists is assumed to be 75%, and we believe the NPV of endoscopist plus CADx will be 90%. To achieve this with an 80% power and significance level (alpha) of 0.05, we will need to assess 200 diminutive recto-sigmoid (100 per group) polyps (588 total polyps), in an estimated 168 patients. We will plan to over recruit by 10% to allow for incomplete data (220 diminutive recto-sigmoid polyps, 647 total polyps). Interim analysis will be done after 50% recruitment

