## 11.4 Study Assessments

Baseline characteristics will be recorded for all participants. Basic demographics will be recorded to include:

- Age
- Sex
- Co-morbidities and ASA score
- History of previous polyps/bowel conditions

During the colonoscopy the following will be recorded in all patients:

- Endoscopist including level of experience (number of life time procedures)
- Indication
- Bowel preparation used and quality
- Use of sedation/general anaesthetic
- Procedure start and finish time and time of maximal intubation
- Comfort score
- Adverse events
- Polyps detected to include the endoscopists optical diagnosis and assessment of size, morphology using the Paris classification, site and details of their removal.
- Still image/video of polyp (where available)

For patients randomised to colonoscopy plus CAD the following additional data will be recorded:

- Total number of potential polyps identified by CADe
- CADx diagnosis of polyps identified
- Outcome of assessment by endoscopist e.g. confirmed as polyp, characterisation assessment

Post colonoscopy:

- Adverse events will be recorded
- Histology of any polyps removed will be recorded to correlate with the endoscopist/CADx assessment of the lesion.

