#### 14.2 Analysis of Endpoints

The primary outcome, ADR, will be compared between groups using the Chi-square test. The difference in the proportion of patients with an adenoma detected between groups will be quantified, along with a corresponding 95% confidence interval.

Within both groups, a descriptive analysis of percentage of polyps correctly identified, relative to the histological diagnosis, will be reported.

For all detection outcomes, a series of sensitivity analyses will be performed, repeating the analyses, but this time only considering polyps in the CAD intervention group if they were correctly identified based on their histology.

Binary secondary outcomes will be analysed using the Chi-square test. Continuous secondary outcomes will be compared between groups using the unpaired t-test, if found to be normally distributed, or the Mann-Whitney test otherwise.

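### The operating endoscopist is not named before an unmaskable allocation is released, so operator choice within a site could depend on arm and could not later be told from chance

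*Protocol*

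**What the plan says.** On timing, Protocol 11.3 says "Randomisation will be carried out prior to the procedure being started". On balance, it says "The randomisation will be stratified by site to ensure an equal allocation in each centre", with varying block sizes; no other stratification factor is named.

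Protocol 11.4 gives a short list of baseline characteristics, and the operator is not on it. The item "Endoscopist including level of experience (number of life time procedures" comes instead at the head of the list of things captured during the colonoscopy.

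Protocol 14.2 fixes the main comparison: "The primary outcome, ADR, will be compared between groups using the Chi-square test". Operator experience is used only to break down the secondary diagnostic-performance measures (8.2), not for ADR.

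Protocol section 10 gives the ADR assumptions. As a percentage, "the ADR of competent but non-expert endoscopists is assumed to be 20", and "we believe that CADe will increase it to 30% (expert level" is how it describes the target with the device.

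No section describes masking, requires the operator to be named before allocation, or says what happens if the operator changes afterwards.

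**The concern.** Randomisation protects the comparison from factors settled before the allocation is known. Here the person performing the procedure, on whom ADR plausibly depends, need not be settled by then. The device cannot be hidden from the operator, so an openly known arm could influence who takes the case. Stratifying by site does not prevent this, because the shift would occur between operators inside a site.

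If it happened, a difference in operators would appear as a device effect or would mask one. Because the operator is recorded only after allocation, the data would hold no record of who had been due to perform the case. The trial could not then separate steering from chance imbalance. Later analysis cannot fully repair this, since the operator who actually performed the case would itself be a post-allocation variable.

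**Working it through.** **Inputs from the protocol.** Section 10: ADR 20% for competent non-experts; 30% with CADe, labelled as expert level; "In order to demonstrate a difference of 10% between the two groups"; "with an 80% power and a significance level (alpha) 0.05"; 294 per group. Sidedness is not stated.

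**Inputs assumed.** Half the operators are expert overall. Experts and non-experts in this trial differ by the full 30% − 20% = 10 points. The expert share differs between arms by d = 10, 20 or 30 points.

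**Step 1: reproduce the planned size.** Two-sided 5%, pooled variance under the null, no continuity correction:

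n = [1.96 × √(2 × 0.25 × 0.75) + 0.8416 × √(0.20 × 0.80 + 0.30 × 0.70)]² / 0.10² = 293.2, so 294 per arm and 588 in total.

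This matches exactly, and 588/0.9 = 653.3 gives the stated maximum of 654. Power at 294 per arm is 80.1%. The sample size is not in question.

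**Step 2: spurious ADR difference with no device effect.** ADR in an arm = 0.20 + 0.10 × expert share, with shares 0.50 − d/2 and 0.50 + d/2. The difference is 0.10 × d.

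**Step 3: probability that the two-sided 5% test rejects at 294 per arm.** With SE₀ = √(2 × 0.25 × 0.75/294) = 0.0357 under the null and SE₁ from the two separate rates:

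P = 1 − Φ[(1.96 × SE₀ − diff)/SE₁] + Φ[(−1.96 × SE₀ − diff)/SE₁]

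For d = 20 points, SE₁ = 0.0357 and P = 1 − Φ(1.40) + Φ(−2.52) = 0.0807 + 0.0059 = 0.0866.

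| Difference in expert share | ADR by arm | Spurious difference | Rejection rate |
|---|---|---|---|
| 0 | 25.0% v 25.0% | 0 | 5% |
| 10 points | 24.5% v 25.5% | 1 point | 5.9% |
| 20 points | 24.0% v 26.0% | 2 points | 8.7% |
| 30 points | 23.5% v 26.5% | 3 points | 13.4% |

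**Step 4: dependence on the 50% share.** If one arm had no experts and the other 10%, 20% or 30% (ADR 20% v 21%, 22% or 23%), the same formula gives 6.0%, 9.1% and 14.3%. The result depends on the size of the imbalance and the ADR gap, and little on the overall share.

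**Step 5: the opposite direction.** Taking 2 points off the planned contrast (20% v 28%) lowers power from 80.1% to 62.3%.

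**Step 6: precision gain from adjustment.** Total variance at a 50:50 mix is 0.25 × 0.75 = 0.1875. Mean within-group variance is (0.16 + 0.21)/2 = 0.1850. Adjustment removes 0.0025/0.1875 = 1.3%, equivalent to about 8 of 588 patients.

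**The case against.** The list in 11.4 shows when the form is filled in, not when an item is decided. Indication and bowel preparation are on the same list and are settled before the procedure starts. Patients are already booked (11.1 Recruitment) and consent on the day, so local lists may well fix the operator. All study endoscopists are to be trained on the device and have access to it (9.1), which weakens any idea that device cases need a particular person. All of this stands. What remains is that no rule makes it so across seven sites in three countries.

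A reader might infer that operators will be steered by arm. The documents do not support that. Without steering, randomisation balances operators on average, chance imbalance is already inside the 5% error rate, and the unadjusted Chi-square test is valid.

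A reader might also infer from section 10 that operator skill in this trial is worth as much ADR as the device. The protocol attaches the expert label to the target rate. It does not say that experts will operate here or that participating operators differ by 10 points. A half-expert pool would also imply a control ADR of 0.5 × 20% + 0.5 × 30% = 25%, not the planned 20%.

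Covariate adjustment is often left to a statistical analysis plan, which might add it. The order in which operator and allocation are entered is trial conduct, which such a plan cannot change after the event.

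**Conclusion.** The point holds as an open route for bias that is cheap to narrow. It is not a demonstrated bias, and the planned test and sample size are not wrong. That the allocation is open is inferred from the nature of the device and the absence of any masking.

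The false-positive rates of about 6%, 9% and 13% are conditional on the assumed 10-point gap, the assumed half-expert pool and the assumed imbalances. The smallest imbalance barely moves the error rate, and the largest would need a systematic 30-point shift pooled over all sites. Precision is not a strong argument, as the gain is about 1% of variance. The reason to act is that, as written, the trial could neither show that allocation had no influence on who operated nor detect it if it had.

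**What to change.** **In 11.3:** require the planned operating endoscopist's study ID and experience level to be entered in REDCap before the allocation is shown. State that allocation must not be a reason to change operator, and log any change with its reason.

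**In 14.2:** estimate the ADR difference adjusted for the pre-entered experience level and for site, the randomisation stratum. Report operator changes by arm, and add a sensitivity analysis by the endoscopist who actually performed the procedure. That last analysis conditions on something that can follow allocation, so it should stay a sensitivity analysis.

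Pre-entry makes switching visible and may deter it. It does not remove the effect of a switch that has happened, which is why the rule against allocation-driven changes and the log are both needed.

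**Cost:** a mandatory pre-randomisation entry for operator and experience, a short change log, and a covariate that is already collected. The sample size is unchanged. The one practical downside is that the operator must be known before the patient is randomised.

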## 9.2 Overall Description of Study Participants

All patients who are undergoing a colonoscopy at one of the participating sites will be screened, and those who meet eligibility criteria below will be invited to participate.

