## 9.3 Eligibility Criteria

Inclusion

• Adults over age 18 who are undergoing a colonoscopy

• Must be able to give informed consent

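### The primary ADR comparison in 14.2 is unadjusted: valid, but less precise than site and the recorded patient characteristics would allow

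*Protocol*

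**What the plan says.** - **Who enters.** Protocol 9.3 admits "Adults over age 18 who are undergoing a colonoscopy", and 9.2 adds that "All patients who are undergoing a colonoscopy at one of the participating sites will be screened". The exclusions in 9.3 include polyposis and active inflammation, but do not limit entry to screening, surveillance or symptomatic patients.
- **How they are allocated.** Section 11.3: "Participants will be randomised electronically in a 1:1 ratio into two groups". Site is the only stratification factor ("The randomisation will be stratified by site to ensure an equal allocation in each centre"), and "a blocked randomisation, with varying block sizes, will be performed" within that scheme.
- **What is recorded.** Section 11.4 lists age, sex and "History of previous polyps/bowel conditions" among the baseline items. It lists indication among the items recorded during the colonoscopy. All are to be recorded for every participant.
- **How ADR is analysed.** Section 14.2: "The primary outcome, ADR, will be compared between groups using the Chi-square test". It continues: "The difference in the proportion of patients with an adenoma detected between groups will be quantified, along with a corresponding 95% confidence interval". No covariate is named, and neither is site.
- **What was planned.** Section 10 assumes an ADR of 20% in the control arm and 30% with the device, 80% power and alpha 0.05. This gives 294 per group, 588 in total, with recruitment up to 654.

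**The concern.** Two kinds of information are available for the primary comparison and neither is used.

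The first is site, which the randomisation is stratified by. Stratifying makes the arms more alike than simple randomisation would. An analysis that ignores the strata takes no credit for this, so its interval is somewhat too wide if sites differ in ADR.

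The second is patient characteristics. With intake this open, patients within one site may differ considerably in their chance of having an adenoma. Stratifying by site does not remove that variation. If indication, age, sex or previous polyps predict adenoma, an adjusted analysis gives a narrower interval for the same overall risk difference from the same patients.

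At stake is the precision of one primary endpoint in a trial planned at 80% power, with over-recruitment meant only to cover losses. The protocol itself names the primary test and effect measure, so this is a choice it has made and not a detail it has left open.

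**Working it through.** **Step 1: reproduce the plan's figure.** Inputs from section 10: p0 = 0.20, p1 = 0.30, 80% power, alpha 0.05. Sidedness is not stated; two-sided reproduces the number. With pooled variance and no continuity correction:

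n per arm = [1.960 × √(2 × 0.25 × 0.75) + 0.842 × √(0.20 × 0.80 + 0.30 × 0.70)]² / 0.10² = (1.200 + 0.512)² / 0.01 ≈ 293.2, rounded up to **294 per arm, 588 in total**.

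588 / 0.90 = 653.3, rounded up to **654**. Both match. The sample size is right for the unadjusted test.

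**Step 2: unadjusted precision.** Per-patient variance of the difference: V0 = 0.20 × 0.80 + 0.30 × 0.70 = 0.37. SE = √(0.37/294) = 0.0355, about 3.5 points. Power = Φ(0.10/0.0355 − 1.96) = Φ(0.859) ≈ 80.5% (80.1% with the pooled-variance test).

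**Step 3: precision after adjusting for indication.** The documents give no indication mix and no ADR by indication, so the following are assumptions:
- two indication groups, the higher-yield one being 30% or 50% of patients;
- a control-arm ADR gap between the groups of 10, 20 or 30 points;
- overall ADR held at the planned 20% vs 30%, with a common odds ratio across groups;
- 294 per arm and the indication mix taken as fixed.

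For the risk difference standardised over the groups, V1 = Σ w [p0(1 − p0) + p1(1 − p1)], where w is the share of each group. The variance ratio is V1/V0, the equivalent N is 588 × V1/V0, and power is Φ(0.10/√(V1/294) − 1.96).

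Worked case (50% share, 20-point gap): control ADR 10% and 30%, device ADR 16.6% and 43.4%. V1 = 0.5 × (0.090 + 0.210) + 0.5 × (0.138 + 0.246) = 0.342. Ratio 0.342/0.37 = 0.924. SE = √(0.342/294) = 0.0341. Power ≈ 83.4%.

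| Higher-yield share | Gap (points) | Control ADR (%) | Device ADR (%) | Variance ratio | Equivalent N | Power at 588 (%) |
|---|---|---|---|---|---|---|
| 30% | 10 | 17 / 27 | 26.1 / 39.0 | 0.985 | 579 | 81.1 |
| 30% | 20 | 14 / 34 | 22.4 / 47.7 | 0.941 | 553 | 82.8 |
| 30% | 30 | 11 / 41 | 18.7 / 56.4 | 0.868 | 511 | 85.7 |
| 50% | 10 | 15 / 25 | 23.4 / 36.6 | 0.981 | 577 | 81.2 |
| 50% | 20 | 10 / 30 | 16.6 / 43.4 | 0.924 | 544 | 83.4 |
| 50% | 30 | 5 / 35 | 9.2 / 50.8 | 0.822 | 483 | 87.5 |

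This covers indication alone. Any gain from site, age, sex and previous polyps is not quantified, because the documents give nothing to base it on.

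**Step 4: chance imbalance.** Without stratification by indication, the between-arm difference in the higher-yield share has a 95% range of ±1.96 × √(2q(1 − q)/294), where q is that share: ±7.4 points for q = 0.3 and ±8.1 points for q = 0.5. Multiplied by the ADR gap averaged over the two arms, this shifts the ADR difference by 0.8-0.9, 1.7-1.9 or 2.5-2.9 points for the three gaps. The unadjusted 95% CI has a half-width of about 1.96 × 3.55 ≈ 7.0 points and already includes this variation.

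**The case against.** The strongest reply is that nothing here is wrong. Randomisation makes the unadjusted comparison unbiased, the Chi-square test controls the type I error, and it is the test the sample size was built on. Stratifying by site with permuted blocks is an accepted design. All of this stands.

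A second reply is that adjusted analyses often sit in a statistical analysis plan, which is not available here. This stands in part: such a plan may well add one. But 14.2 already fixes the primary test and effect measure, and 14.4 sends deviations from the original plan through the Trial Steering Committee. An adjusted analysis added elsewhere would therefore be secondary unless 14.2 is changed.

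A third reply is that the gain could be trivial. This also stands as a possibility. At a 10-point gap it is about 2% of the variance and about one point of power, and no document says how strongly indication predicts adenoma.

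Three stronger readings are tempting, and the documents do not support them:
- **That the ADR result would be biased or underpowered.** It would not be; 588 is correct for the planned test.
- **That chance imbalance in indication is a further harm.** It is the same variance as the loss of precision, seen from another side, and the unadjusted interval already covers it.
- **That indication should have been a stratification factor.** Section 11.4 lists it among data recorded during the procedure, whereas 11.3 randomises before the procedure starts. Seven sites by three indications would give 21 strata for at most 654 patients, about 31 each and fewer at small sites. Varying block sizes do not cure incomplete blocks. With 294 per arm, adjustment in the analysis recovers nearly all of the precision without this.

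**Conclusion.** The point holds as one of efficiency. The primary ADR analysis leaves out the factor that randomisation was stratified by and the patient characteristics that the trial records anyway, so its estimate is less precise than the data allow. Validity and the stated sample size are not in question.

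On the assumptions in the working, using indication is worth about 2% to 18% of the variance, or roughly 1 to 7 points of power at 588 patients. The low end is negligible and the high end material. Which applies depends on the case mix and on the ADR gap between indications, and the documents give neither. The change is worth making because it needs no extra patients or variables, not because the present analysis is defective.

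**What to change.** In 14.2, make the primary ADR estimate a risk difference with 95% CI, standardised from a logistic model that includes arm, site, indication, age, sex and previous polyps. Keep the unadjusted Chi-square test and crude difference as supportive. Define indication as the referral reason known before the procedure, so that nothing seen during the examination can influence the covariate. Leave 11.3 as it is.

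**Cost.** Slightly more analysis work and a primary estimate that depends on a model. The model is modest for the data: at the planned rates about 294 × 0.20 + 294 × 0.30 = 147 patients would have an adenoma, against about 12 coefficients besides the intercept (arm 1, seven sites 6, indication in three categories 2, age 1, sex 1, previous polyps 1). No new data items are needed. The one procedural point is to take indication from the referral, which should be available because 11.1 screens patients from booked procedures.

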## 11.4 Study Assessments

Baseline characteristics will be recorded for all participants. Basic demographics will be recorded to include:

- Age
- Sex
- Co-morbidities and ASA score
- History of previous polyps/bowel conditions

During the colonoscopy the following will be recorded in all patients:

- Endoscopist including level of experience (number of life time procedures)
- Indication
- Bowel preparation used and quality
- Use of sedation/general anaesthetic
- Procedure start and finish time and time of maximal intubation
- Comfort score
- Adverse events
- Polyps detected to include the endoscopists optical diagnosis and assessment of size, morphology using the Paris classification, site and details of their removal.
- Still image/video of polyp (where available)

For patients randomised to colonoscopy plus CAD the following additional data will be recorded:

- Total number of potential polyps identified by CADe
- CADx diagnosis of polyps identified
- Outcome of assessment by endoscopist e.g. confirmed as polyp, characterisation assessment

Post colonoscopy:

- Adverse events will be recorded
- Histology of any polyps removed will be recorded to correlate with the endoscopist/CADx assessment of the lesion.

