## 8.1 Summary of Study Design

This will be a multi-centre randomised control superiority trial. Participants will be randomised to either standard colonoscopy (control arm) or colonoscopy plus WISE VISION® CAD device (intervention arm). The CAD device has both detection and characterisation functions and there are 2 elements within the study. Firstly the study will aim to assess the impact of computer aided detection and secondly computer aided characterisation.

When polyps are identified, these will be recorded and the endoscopist will be required to assess this and indicate their optical diagnosis accordingly. For patients randomised to colonoscopy plus CAD, the CADx will then be carried out and the results recorded. Polyps will be treated according to standard care.

Polyps detected by the endoscopists but missed by the CADe device will also be recorded. The total number of polyps identified and the endoscopist diagnosis will be recorded for both arms. The histology results of the polyps removed will be collected.

Figure 1: Study Procedure Flowchart

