## Secondary End points

COLOVISION Protocol v1.0 18/08/2022 IRAS ID: 313559 Polyp detection rate (PDR) in both groups

Adenoma per colon (APC) in both groups

PIVI-1: agreement between surveillance interval decisions based on histology and that based on the combination of histology of non-diminutive polyps and optical diagnosis in both arms

Diagnostic performance measures in both groups (sensitivity, specificity, accuracy, NPV, PPV, AUC)

Diagnostic performance measures in both groups (sensitivity, specificity, accuracy, NPV, PPV, AUC) according to endoscopists experience

Diagnostic performance measures in both groups (sensitivity, specificity, accuracy, NPV, PPV, AUC) according to endoscopy imaging mode (WLI or EI)

The proportion of histological assessments that could have been avoided in both arms

The proportion of polyp removals that could have been avoided in both arms

Withdrawal time in both groups

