# **13. DATA HANDLING AND RECORD KEEPING**

## 13.1 Data Collection

Patients will be allocated a unique anonymised study ID number, in which their data will be collected against, to maintain participant confidentiality. A paper Case Report Form (CRF) will be created for data collection for those participating in the trial. This will be contemporaneously populated by a delegated member of the research team during the procedure. This will then be uploaded onto the REDCap database by a delegated member of the research team. Query reports will be run on the database regularly throughout the study and where data is missing or incorrect this will be chased. Missing/incorrect data will also be reviewed and discussed at the Trial Steering Meetings.

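### Withdrawal time, as recorded, mixes inspection with polyp work and a CADx step that exists in one arm only, so a between-arm difference cannot be read as a difference in inspection time

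*Protocol*

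**What the plan says.** The protocol lists "Withdrawal time in both groups" among the secondary endpoints (section 8.2, and likewise in the synopsis) and does not say what the term covers.

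Section 11.4 sets out what is recorded during colonoscopy. The timing item, common to both arms, is "Procedure start and finish time and time of maximal intubation". For polyps, the list includes "morphology using the Paris classification, site and details of their removal", but no duration. Images or video are of the polyp and are kept only where available. The additional CAD-arm items include "CADx diagnosis of polyps identified", again without a time.

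Section 8.1 describes the sequence. The endoscopist states an optical diagnosis for each polyp, and then: "For patients randomised to colonoscopy plus CAD, the CADx will then be carried out and the results recorded". On removal it says: "Polyps will be treated according to standard care".

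Section 14.2 compares continuous secondary outcomes between arms by an unpaired t-test or a Mann-Whitney test, with no adjustment.

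**The concern.** A withdrawal time that includes polyp work answers a different question from one that measures inspection. If the CAD arm turns out longer, there are at least three explanations:

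- endoscopists inspected more slowly, which is one route by which ADR could rise;
- they assessed and removed more polyps, which is a consequence of a higher ADR;
- they spent time on the CADx step, which is a workload cost.

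The endoscopist knows whether the device is running, so readers will ask whether a gain in ADR came with longer inspection. This is the endpoint they will turn to, and the listed data do not let it answer. This is a matter of data capture. An analysis plan can choose a definition, but it cannot recover a duration that nobody wrote down.

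**Working it through.** **What the listed times yield.** Start to maximal intubation is the insertion phase. Maximal intubation to finish is the only available withdrawal interval:

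withdrawal time = finish − maximal intubation = inspection + polyp assessment + removal + (CAD arm only) CADx

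With equal inspection time in both arms, the expected difference is

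CAD − control = CADx time + time to assess and remove any extra polyps.

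Both terms are positive under the protocol's own expectations. Section 8.1 gives the first and section 10 (ADR 20% against 30%) makes the second likely. Polyps removed on insertion fall outside the interval.

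**The protocol's own sample size, reproduced.** For 20% against 30%, two-sided alpha 0.05 (two-sided is assumed) and 80% power:

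n = [1.96·√(2·0.25·0.75) + 0.842·√(0.20·0.80 + 0.30·0.70)]² / 0.10² = (1.200 + 0.512)² / 0.01 ≈ 293.2, so 294 per group and 588 in total.

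588 / 0.90 = 653.3, so 654. Both figures agree with section 10. No figure is given for withdrawal time.

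**Illustration of size.** Inputs:

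- Patients per arm: 294 (section 10).
- Polyps per patient: 1 (assumed), or 588 / 168 = 3.5, the ratio implied by the CADx paragraph of section 10. Applying 3.5 to every patient is itself an assumption.
- CADx step: 10, 20 or 30 seconds per polyp (assumed; no duration is given).
- SD of withdrawal time: 4, 6 or 8 minutes (assumed; none is given).

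Added minutes d = polyps × seconds / 60. The chance of a significant result in the direction of longer with CAD, when inspection time is identical, is Φ(d / (SD·√(2/294)) − 1.96). With no difference at all it would be 2.5%.

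| Polyps per patient | Seconds per polyp | d (min) | SD 4 | SD 6 | SD 8 |
|---|---|---|---|---|---|
| 1 | 10 | 0.17 | 7% | 5% | 4% |
| 1 | 20 | 0.33 | 17% | 10% | 7% |
| 1 | 30 | 0.50 | 33% | 17% | 11% |
| 3.5 | 10 | 0.58 | 42% | 22% | 14% |
| 3.5 | 20 | 1.17 | 94% | 65% | 42% |
| 3.5 | 30 | 1.75 | about 100% | 94% | 76% |

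Example, last cell: 8·√(2/294) = 0.66; 1.75 / 0.66 = 2.65; 2.65 − 1.96 = 0.69; Φ(0.69) ≈ 0.76.

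**Extra polyps.** An assumed 0.1 to 0.5 extra polyps per patient at an assumed 1 to 3 minutes each adds 0.1 × 1 = 0.1 to 0.5 × 3 = 1.5 minutes. The lower count corresponds to one adenoma in each newly positive patient: 0.30 − 0.20 = 0.10 per patient.

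**The case against.** Five points can be made on the other side.

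*The list in 11.4 may not be complete.* The case report form is not shown and could hold more time fields. That is so, and the point is limited to what the protocol lists. It lists none.

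*Total time is a legitimate measure.* Section 7.2 includes the cost implications of the device among the secondary objectives, and for that purpose time spent on CADx or on extra removals is a real effect. The protocol also never says that withdrawal time is meant to test for slower inspection. This stands, and it is why total time should be kept. It does not make the single undefined measure interpretable as inspection time.

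*The data are not wholly uninformative.* Every polyp is recorded, so withdrawal time can be described by number of polyps removed or in patients with none. Both condition on what happened after randomisation, and the device affects both. They are supportive only.

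*The size rests on assumptions.* It does. If CADx takes a few seconds and few extra polyps are removed, the effect may be negligible.

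*A paused clock has its own error.* Someone in an unblinded room must judge when inspection stops, and CADe prompts that prove not to be polyps occur in one arm only. This is a fair criticism, and the fix needs a rule for it.

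A reader might go further and infer that the ADR result is itself biased. The documents do not support that. ADR is compared between randomised groups, and slower inspection prompted by the device would be part of its effect.

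**Conclusion.** The point holds for the secondary endpoint. On the items listed in section 11.4, withdrawal time includes polyp assessment, removal and a CADx step present in one arm only. It is therefore expected to be longer with CAD even at equal inspection time, and the endpoint cannot tell slower inspection from more removals or added workload.

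The direction is an expectation under the protocol's own assumptions. It would be tempting to say that the CAD arm is bound to show a longer or significantly longer time, but the documents give no per-polyp durations and no SD. On the assumed inputs, the chance of a significant difference from the CADx step alone runs from about 4% to nearly 100%, so the size is not established.

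The primary ADR comparison is unaffected. The change is worth making because it is cheap and cannot be made after the data are collected.

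**What to change.** **Section 11.4.** Add one field in both arms: cumulative time during withdrawal spent on polyp assessment, removal and, in the CAD arm, CADx. State that time spent examining CADe prompts not confirmed as polyps counts as inspection, so that all sites stop the clock in the same way.

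**Section 8.2.** Define inspection withdrawal time (finish minus maximal intubation, less the recorded time) as the endpoint, and keep total withdrawal time as a separate workload measure.

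If withdrawal time in patients with no polyp is also reported, label it as supportive, because that group is formed after randomisation.

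**Cost.** One case report form field and two sentences of protocol text. The form is already completed in the room; section 13.1 says: "This will be contemporaneously populated by a delegated member of the research team during the procedure". The downside is a little timing effort and some measurement error, since the person holding the clock knows the allocation.
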